13.5.3 Secondary Analyses

Both efficacy and toxicity rates will be estimated using simple relative frequencies. The corresponding 95% confidence intervals for the estimated probabilities will be computed using the method proposed in Clopper and Pearson (1934). The relationship between binary outcomes and collected demographic and baseline variables will be statistically assessed using logistic regression in an exploratory fashion. Maximum likelihood estimation will be utilized in the model fitting procedures as implemented by SAS PROC LOGISTIC. Wald tests of the model effects will be performed to assess statistical significance; see SAS documentation for details. See Hosmer and Lemeshow (2000) for a discussion of such techniques. Alternative parametric models will be considered if model fit is found to be inadequate.

The estimated distributions of overall and progression free survival will be obtained using the Kaplan-Meier method. Estimates of quantities such as median survival will be obtained. Corresponding confidence intervals using the methodology of Brookmeyer and Crowley (1982) will be computed. It is assumed a priori that any drop out times will be non-informative in terms of the censoring mechanism. Groups defined by levels of categorical or dichotomized numeric demographic/baseline variables will be compared in regards to time-to-event distributions using the log-rank test. Cox proportional hazards model regression will be utilized for multivariate analyses.

All tests will be two-sided and tested at a 0.05 nominal significance level. Standard diagnostic plots will be used to assess model fit and transformations of variables may be considered in order to meet statistical assumptions.

The analysis will be performed using the SAS® statistical software system.

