3.3. Secondary Objectives

- To determine the feasibility of successful mobilization of autologous stem cells (i.e., minimum of 2×10^6 CD34+ cells/kg should be collected) to be used for ASCT (if applicable).
- To determine toxicities associated with C-R-ICE salvage therapy.
- To determine the TTP, PFS, and OS followed by ASCT (if applicable); Disease-free survival in CR patients.
- To determine the pharmacokinetics/pharmacodynamics relationship between carfilzomib's degree of proteasome inhibition and response rate along with the time course of thrombocytopenia.
- To study differences in clinical outcomes between GCB and non-GCB relapsed/refractory DLBCL following therapy with carfilzomib and R-ICE.

[figure not shown]
Correlative translational research studies to include: phenotypic/genotypic analysis and functional activity (i.e., ADCC and CMC) of patient's peripheral blood mononuclear "effector" cells (PBMC), as well as ex vivo analysis of sensitivity of primary tumor cells to various combinations of carfilzomib versus Bortezomib +/- rituximab; enzymatic assay for chymotrypsin-like activity to determine the degree of proteasome inhibition in primary DLBCL patient samples and patient PBMC specimens; explorative analysis to identify potential factors predictive of response to therapy will be performed (as part of an NIH-supported R01 grant: R01 CA136907-0A1; PI: [name]).

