13.1.2 Phase Ib

The sample size calculation for the Phase Ib population is based on testing the hypotheses concerning the proportion of the population who experience an objective response (i.e., CR or PR) described above. This design requires a total of up to 30 patients in order to achieve approximately 80.1% power to detect differences of 20 percentage points (50% versus 70%).

Based on the excellent response observed in the patients treated in the Phase I portion (ORR 90%) and budget changes, the sample size for the Phase Ib portion was reduced. The phase Ib portion will include 9 additional patients. The efficacy analysis will include evaluable patients in the Phase I and Phase Ib portions combined (sample size up to 45). The sample size calculation for the efficacy analyses is based on testing the hypotheses concerning the proportion of the population who experience an objective response (i.e., CR or PR) described above. This design requires a total of up to 30 patients in order to achieve approximately 80.1% power to detect differences of 20 percentage points (50% versus 70%).

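### Response is recorded on four ordered levels but related to baseline variables only by Wald logistic regression on binary outcomes, which makes an ORR comparison uninformative if response stays near 90%

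*Combined protocol and SAP*

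**What the plan says.** Section 10.3 classifies each patient as CR, PR, SD or PD, which is an ordered scale. For relating outcomes to patient characteristics, Section 13.5.3 says: "The relationship between binary outcomes and collected demographic and baseline variables will be statistically assessed using logistic regression", and labels this exploratory. It adds that "Wald tests of the model effects will be performed to assess statistical significance" and that "All tests will be two-sided and tested at a 0.05 nominal significance level". The only fallback is conditional on poor fit: "Alternative parametric models will be considered if model fit is found to be inadequate". Time-to-event outcomes by categorical baseline group go to the log-rank test and Cox regression. Efficacy rates get Clopper-Pearson intervals.

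Section 3.3 lists as a secondary objective "To study differences in clinical outcomes between GCB and non-GCB relapsed/refractory DLBCL following therapy with carfilzomib and R-ICE", together with an exploratory search for predictors of response. It gives no subgroup rates, subgroup sizes or power. Cell of origin is determined by the Hans algorithm (Section 9.2 and the study calendar notes).

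Section 13.1.2 explains the smaller expansion cohort with the words "Based on the excellent response observed in the patients treated in the Phase I portion (ORR 90" (the figure is a percentage).

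**The concern.** A binary split of response at CR+PR discards the difference between CR and PR and between SD and PD. A split at CR merges the three lower levels. The CR+PR cut is needed for the primary comparison with a historical rate, but nothing in the plan requires it for comparing groups within the trial.

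The problem is sharpest at the response rate the plan reports. With about 90% responding, nearly all patients fall on one side of the CR+PR split, and the Wald statistic performs poorly in such sparse tables. Poor model fit would not flag this, so the fallback clause would not be triggered. The risk is that a comparison with no realistic chance of significance is reported as showing no difference between GCB and non-GCB disease, or no predictive value for a baseline factor.

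**Working it through.** **Plan's own figure.** The plan states no power for these analyses. Its 80.1% power and 4.8% type I error belong to the primary single-arm test. An exact one-stage rule with 30 patients (success at 20 or more responses) gives 73.0% and 4.94%, so the stated pair is not reproduced at that size. That is a separate matter and is not used below.

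**Inputs from the documents.** Two-sided 0.05 and Wald tests (13.5.3); up to 30 evaluable patients (13.5.2), although 13.1.2 also mentions 45; 50% and 70% (13.1.2, 13.5.2), which describe the whole cohort against a historical control; ORR 63% and CR 38% with R-ICE or R-DHAP (Section 2); observed ORR 90% (13.1.2).

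**Assumptions.** Subgroup splits of 15/15, 18/12 and 20/10; a common odds ratio across the cut-points; non-responders divided equally between SD and PD.

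**Step 1: smallest attainable Wald p for ORR.** At 90% of 30 there are 3 non-responders, *a* in a group of size n1 and *b* in a group of size n2. Then z = ln[a(n2−b) / (b(n1−a))] / √(1/a + 1/(n1−a) + 1/b + 1/(n2−b)). The most extreme table without an empty cell has a = 1, b = 2:
- 15/15: ln(13/28) = −0.767, SE 1.284, z = −0.60, p = 0.55.
- 18/12: ln(10/34) = −1.224, SE 1.288, z = −0.95, p = 0.34.
- 20/10: ln(8/38) = −1.558, SE 1.295, z = −1.20, p = 0.23.

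With a = 0, b = 3 the odds ratio estimate is infinite and the Wald test is unusable.

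This result is specific to response near 90%. With 6 non-responders (80%) and a = 1, b = 5, the minimum is 0.097 at 15/15, but ln(7/85)/1.184 = −2.11 gives 0.035 at 18/12, and ln(5/95)/1.205 = −2.44 gives 0.015 at 20/10.

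Changing the binary test helps only so far. For 0 versus 3 non-responders, Fisher's two-sided p is 2 × 455/4060 = 0.224 at 15/15, 220/4060 = 0.054 at 18/12 and 120/4060 = 0.030 at 20/10.

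**Step 2: power.** Simulation at 15/15 with 100,000 trials per row. The ordinal test is the tie-corrected Wilcoxon test; an empty cell counts as non-significant for Wald. The odds ratio 2.33 is (0.70/0.30)/(0.50/0.50). Entries are percentages.

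| Setting | Ordinal | ORR Wald | ORR score | CR Wald | Ordinal minus ORR Wald |
|---|---|---|---|---|---|
| ORR 50 v 70, CR 38 in lower group, OR 2.33 | 23 | 17 | 20 | 19 | 6 |
| ORR 63, CR 38 in lower group, OR 2.33 | 23 | 9 | 18 | 19 | 13 |
| Centred on ORR 70, CR 38, OR 2.33 | 23 | 11 | 19 | 16 | 12 |
| Centred on ORR 70, CR 38, OR 4 | 51 | 27 | 40 | 37 | 25 |
| Centred on ORR 90, CR 50 (assumed), OR 4 | 48 | 0.4 | 14 | 43 | 48 |
| ORR 50 v 70, CR 38 in both groups | 9 | 17 | 19 | 4 | −8 |

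**Step 3: other splits and sizes.** In the second row the gain over ORR Wald rises to 14.7 points at 18/12 and 16.4 at 20/10. In the first row it is 6.4 and 7.1. With 45 patients (23/22), the first row gives ordinal 32.2, ORR Wald 25.9 and CR Wald 25.3.

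**Step 4: source of the gain.** Replacing Wald by the score test on the same binary ORR recovers about 3 of the 6 points in the first row (20 − 17), 9 of 13 in the second (18 − 9) and 14 of 25 in the fourth (26.7 to 40.4, out of 26.7 to 51.4). The rest comes from keeping the four levels. Under the null at ORR 70%, Wald on ORR rejects about 2.5% of the time and the ordinal test about 5%.

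**The case against.** Logistic regression on ORR and CR is conventional, these are the response measures the protocol uses throughout, and Section 10.1 stresses comparability with earlier DLBCL studies. Section 13.5.3 labels the analysis exploratory, and Section 13 puts the focus on estimation for planning later trials. The term binary outcomes follows a sentence on efficacy and toxicity rates, so it may also cover toxicity, to which the four-level scale does not apply. Section 3.3 speaks of clinical outcomes in general, and GCB status can be tested on survival by log-rank and Cox methods.

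Much of the apparent cost of dichotomising is really the cost of the Wald statistic, and the ordinal advantage reverses when groups differ in PR but not CR. Against a CR split the gain is small: about 4 points in the first two rows of the table, and about 5 in the 90% row. At an odds ratio near 2.3 the ordinal test itself has only about 17% to 33% power across the settings examined.

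All of this stands, and it keeps the point to an inexpensive improvement. It does not answer Step 1, which needs neither an effect size nor proportional odds. Nor does it supply an ordinal analysis that the plan leaves out.

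**Conclusion.** The point holds as a low-cost improvement to an exploratory analysis. If response stays at 90% in 30 patients, the named test on ORR cannot be significant in any non-separated table at the splits examined, so a report of no difference would carry no information. The gain from an ordinal test ranges from about 6 points over Wald ORR (4 over Wald CR) at 50% versus 70%, through 12 to 16 over Wald ORR at the same odds ratio under other overall rates, to a loss of about 8 when CR rates are equal.

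Three stronger readings are tempting, but the documents do not support them:
- A reader might infer a loss of 13 to 25 points at the plan's own rates. Those figures (over CR and ORR respectively) need an odds ratio of 4 at ORR 70%, which implies subgroup ORRs of 82% and 54%. The plan states no subgroup effect, split or SD/PD share.
- A reader might infer that the plan assigns this regression to GCB versus non-GCB. It does not. This is simply the only response-versus-baseline method given.
- A reader might infer that an ordinal test would make the comparison adequately powered. Power stays modest under either method unless the effect is large.

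**What to change.** In Section 13.5.3, state that response by GCB/non-GCB status and by baseline variables is analysed on the ordered scale CR > PR > SD > PD. Use an exact or tie-corrected Wilcoxon test for two groups and a proportional-odds model with a likelihood-ratio test for covariates. Where binary ORR or CR is also tested, replace the Wald test with an exact or likelihood-ratio test. The exact test is the safer choice at very small counts: for 0 versus 3 non-responders at 15/15 the likelihood-ratio p is 0.034, against an exact 0.224. Keep subgroup ORR and CR rates with Clopper-Pearson intervals as description, and name the method for the GCB objective explicitly. The primary ORR test is unchanged.

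The cost is a few sentences and a few lines of SAS. PROC LOGISTIC, already named, fits the cumulative logit model, and no new data are needed. The downside to state is that the ordinal test relies on roughly proportional odds for its power, though the Wilcoxon test stays valid under the null without that assumption.

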13.5 Phase Ib (expansion cohort)

The objective of the Phase Ib component is examination of the efficacy and toxicity of the addition of carfilzomib to R-ICE at the MTD dose.

The primary objective of the Phase Ib component is to assess the efficacy of the study treatment arm as compared to historical control. The primary efficacy endpoint will be best overall response rate (PR+CR) within following 3 cycles of C-R-ICE therapy (as demonstrated by whole body PET-CT and dedicated CT scans following Cycle 3 of therapy).

The efficacy analysis will include patients treated in the Phase I and Phase Ib part of the study. This change in the protocol was decided based on the excellent ORR observed in the first 15 patients treated in the Phase part of the study and changes in the protocol budget.

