13.5.2 Phase Ib Decision Rules

Let π represent the proportion of the evaluable population of interest who experience an overall response within 3 weeks after completion of therapy (i.e., 3 cycles) at the carfilzomib MTD. If the response rate of less than 50% is considered unacceptable. A response rate of more than 70% is considered promising and evidence of such will deem the treatment worthy of further study. The null and alternative hypotheses corresponding to the design are

$$H_0 : \pi \leq 50\%,$$
$$H_a : \pi > 50\%.$$

A total of up to 30 evaluable patients will be accrued in the Phase I and Phase Ib portions of the study. The evaluable population is defined as patients who meet eligibility requirements and complete at least 1 cycle of therapy. Unevaluable patients will be replaced.

With this re-design, the probability is 4.8% of falsely concluding that the proportion of those who experience an overall response exceeds 50% and 80.1% is the probability of correctly concluding efficacy when the overall response rate is 70%.

In the event that the actual first stage sample size is not as planned, the adjustment of the first-stage stopping rule will be based on the approximate minimax rule proposed in Green and Dahlberg (1992): Stop the trial if the number of responses is α or less, where α is the largest value for which power properties would be maintained given the attained first-stage sample size, assuming the planned final sample size is achieved and one applies the planned final boundary. If the planned second stage sample size is not attained, the bound will be adjusted so to preserve Type I error.

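### If response stays near 90%, Wald tests from maximum-likelihood logistic regression can hide a strong binary predictor of response; 13.5.3 names no method for an empty cell

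*Combined protocol and SAP*

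**What the plan says.** Section 13.5.3 (Secondary Analyses) says the relationship between binary outcomes and demographic and baseline variables will be "statistically assessed using logistic regression in an exploratory fashion". It fixes the estimation method, "Maximum likelihood estimation will be utilized in the model fitting procedures as implemented by SAS PROC LOGISTIC", and the test, "Wald tests of the model effects will be performed to assess statistical significance". Tests are two-sided at a nominal 0.05. The only fallback is that other parametric models may be considered if the fit proves inadequate. Separation, penalized likelihood, exact logistic regression and profile-likelihood intervals are not mentioned in the document.

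Section 13.1.2 explains the redesign: "Based on the excellent response observed in the patients treated in the Phase I portion (ORR 90%) and budget changes". Section 13.5 attributes it to the "excellent ORR observed in the first 15 patients treated in the Phase part of the study". On the size of the analysis set, 13.5.2 says "A total of up to 30 evaluable patients will be accrued in the Phase I and Phase Ib portions of the study", while 13.1.2 also gives "sample size up to 45".

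Section 3.3 makes differences in clinical outcomes between GCB and non-GCB disease a secondary objective and plans an exploratory search for factors that predict response.

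**The concern.** When nearly everyone responds, the information about predictors sits in a handful of non-responders. If all of them fall in one level of a binary factor, the 2×2 table has an empty cell. The maximum-likelihood odds ratio is then infinite, the standard error grows faster than the estimate, and the Wald statistic shrinks toward zero. The most striking tables therefore produce the least significant Wald results.

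The fallback does not clearly help. It is triggered by poor fit, which a separated model need not show, and it names no method.

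At stake is the response part of the cell-of-origin objective and the search for predictive factors. A strong predictor of non-response could be reported as non-significant and so misinform the later trials that section 13 says these analyses should help to plan.

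**Working it through.** **Inputs from the documents.** Response 90% (13.1.2); up to 30 evaluable patients (13.5.2), or up to 45 (13.1.2); null and target rates 50% and 70% (13.5.2); two-sided 0.05 (13.5.3). Group splits and subgroup response rates are assumptions, because the documents give none.

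**The 90% figure.** With 15 patients the nearest values are 13/15 = 86.7% and 14/15 = 93.3%, so 90% is either rounded or has another denominator. The exact 95% intervals are 60–98% and 68–99.8%. Both neighbouring rates are therefore checked below, along with 70%.

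**Step 1: chance of an empty cell for a factor with no effect.** With group sizes a and b and common rate p:

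P = 1 − [1 − p^a − (1−p)^a] × [1 − p^b − (1−p)^b]

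- 15/15, p = 0.9: 0.9^15 = 0.2059; P = 1 − 0.7941² = 36.9%.
- 10/20, p = 0.9: 0.9^10 = 0.3487 and 0.9^20 = 0.1216; P = 1 − 0.6513 × 0.8784 = 42.8%.
- 6/24, p = 0.9: 0.9^6 = 0.5314 and 0.9^24 = 0.0798; P = 1 − 0.4686 × 0.9202 = 56.9%.
- Other rates at N = 30, splits 15/15 to 6/24: 58–73% at 93.3%, 22–44% at 86.7%, 1–12% at 70%.
- N = 45, p = 0.9, splits 22/23 to 10/35: 18–37%.
- Simulation at N = 30, 90% response: one continuous null covariate separates in about 5% of trials; two continuous plus two binary covariates in about 54%.

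These figures include the case of no non-responders at all (0.9^30 = 4.2%), which no method can rescue.

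**Step 2: what the tests report with 27/30 responders.** There are C(30,3) = 4060 ways to place the three non-responders.

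- 24/24 versus 3/6: Fisher p = C(6,3)/4060 = 20/4060 = 0.005; Firth penalized likelihood-ratio p = 0.002. Newton iterations for the Wald test give slope 9.20, SE 20.35, p = 0.65 after 8 steps, and slope 16.20, SE 673, p = 0.98 after 15.
- 20/20 versus 7/10: Fisher p = C(10,3)/4060 = 120/4060 = 0.030; Firth p = 0.018; Wald p = 0.71 after 8 steps and 0.98 after 15.
- 15/15 versus 12/15: Fisher p = 2 × C(15,3)/4060 = 910/4060 = 0.22; Firth p = 0.09; Wald uninformative. The ordinary likelihood-ratio test gives 0.034, but its type I error at this split and 90% response is 7.8%, so that result cannot be relied on.
- Tables without an empty cell: at splits 15/15, 12/18, 10/20, 9/21 and 6/24 the smallest Wald p is 0.068.

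**Step 3: power for a real predictor.** All 2×2 tables at N = 30 were enumerated, with overall response 90% in each row. Separated tables count as non-significant for Wald.

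| Response by group | Split | P(empty cell) | Wald | Fisher | Firth |
|---|---|---|---|---|---|
| 60% vs 97.5% | 6/24 | 57% | 20.0% | 61.9% | 61.9% |
| 75% vs 97.5% | 10/20 | 63% | 7.5% | 36.1% | 36.2% |
| 82% vs 98% | 15/15 | 75% | 0.2% | 8.8% | 21.4% |

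**The case against.** Much of the case on the other side stands.

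- The analysis is labelled exploratory. The primary response decision, the Clopper-Pearson intervals and the MTD do not use it. Survival comparisons between GCB and non-GCB groups use the log-rank test.
- The 90% rate comes from a small early group. At the 70% design rate the problem largely disappears.
- In a balanced 15/15 split with three non-responders, the recommended tests also miss 0.05. There the limit is the information in the data, not the choice of test.
- An infinite odds ratio with a huge standard error is conspicuous, and the summaries by baseline variable planned in 13.3 would show the empty cell.

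The last point does not remove the need for a rule. An analyst who notices separation must then choose a replacement test after seeing the data, which a pre-specified sentence avoids.

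Three stronger readings are tempting, and the documents do not support them. A reader might take 37–57% as the chance of missing a real predictor. It is the chance of an empty cell when the factor has no effect, where a non-significant result is correct; Step 3 gives the loss of power. A reader might infer that all the planned logistic regression fails. Single continuous covariates separate rarely, and toxicity outcomes with mid-range rates are much less affected. A reader might also conclude that models must be limited to one covariate at a time, but the fault shown here does not justify so general a rule.

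**Conclusion.** The concern holds in a limited form, at minor severity. If the final response rate is near 90% with 30 patients, a binary factor will often produce an empty cell, and the specified Wald test then cannot detect even a strong association. With exactly 27/30 responders, the Wald test reaches 0.05 in no table at the splits examined. In uneven splits with the non-responders concentrated in the smaller group, Fisher and Firth recover a substantial part of the power: about 62% against 20% in the 6/24 scenario.

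This rests on the 90% rate persisting, on about 30 analysed patients, and on assumed splits and subgroup rates. With 45 patients the problem is smaller, and at 70% response it is uncommon. It concerns exploratory analyses of response by binary or categorical factors; the primary decision, the log-rank comparisons and mid-range toxicity outcomes are largely unaffected.

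**What to change.** In 13.5.3, replace the Wald tests for sparse binary outcomes, meaning any empty cell or few events or non-events. Say that response is expected to be such an outcome, so that the choice does not wait for the data. Possible wording:

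*For response, and for any other binary outcome with an empty cell or few events or non-events, logistic models will be fitted by Firth's penalized likelihood, with penalized likelihood-ratio tests and profile-likelihood intervals (FIRTH and CLPARM=PL in PROC LOGISTIC), or by exact logistic regression. Single binary factors will be tested by Fisher's exact test.*

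The remaining binary outcomes can keep the present method, and no general limit on the number of covariates is needed. The size of the analysis set (30 or 45) should be reconciled at the same time, because the expected number of non-responders depends on it.

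The cost is one sentence and an option in the SAS software already specified, with no extra patients. The downsides are slight shrinkage of the estimates and the conservatism of Fisher's test (type I error 0.5% at 90% response with a 15/15 split).

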Study Design	This is multi-center open-label, prospective Phase I/Ib clinical trial evaluating the safety, efficacy, and pharmacokinetics/pharmacodynamics of Carfilzomib + standard R-ICE combination therapy in adult patients with relapsed/refractory diffuse large B-cell lymphoma. The statistical design is based on a dose-finding algorithm to determine the maximal tolerated dose (MTD) of the study regimen and an assessment of the efficacy of the treatment for patients as compared to an external standard, i.e., R-ICE historical control. All enrolled patients will receive the study drug and initiation of the treatment should take place as soon as possible following study enrollment. A total of up to 30 evaluable patients will be enrolled in the Phase I/Ib component
Target Accrual and Study Duration	A maximum of 21 patients for Phase I and 9 patients for Phase Ib expansion cohort will be enrolled at Roswell Park. The number of subjects required is a function of a currently unknown dose-toxicity relationship. Accrual is expected to take up to 10 years.
Study Procedures	
Disease Evaluation: Prior to study, at time of restaging; between Cycle 2 Day 15 to Cycle 2 Day 28 following Cycle 3 but before ASCT and at the end of treatment evaluation, then every 4 months (± 2 weeks) for 1 year, then every 6 months (± 2 weeks) for 2 years, then once a year (± 2 weeks) for 2 years for a total of 5 years, then as clinically indicated. The follow up period will begin at the end of study evaluation visit for patients that became ineligible for transplant for any reason but did not meet criteria for disease progression. The follow up period for patients that go on to transplant will begin at the Day +100 bone marrow biopsy. Patients that progress at any time will be followed for survival status only on a yearly basis.
 
Adverse Events: From first dose of study drug until 30 days after receiving last dose of study drug.
 
Hematology and Chemistry: Prior to study, Day 1 of each cycle, and post treatment follow-up.
 
Performance Status: Prior to study, Day 1 of each cycle, and post treatment follow-up.
 
History and Physical Examination: Prior to study, Day 1 of each cycle, and post treatment follow-up.
 
Electrocardiogram: Prior to study

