4.2. Target Accrual and Study Duration

A maximum of 21 patients for Phase I and 9 patients for the Phase Ib expansion part of this trial will be enrolled at Roswell Park and Network Sites (For Phase Ib only). The number of subjects required is a function of a currently unknown dose-toxicity relationship. Accrual is expected to take up to 10 years.

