- 3 Prior to study, at time of restaging; between Cycle 2 Day 15 to Cycle 2 Day 28 following Cycle 3 but before ASCT and at the end of treatment evaluation, then every 4 months (\pm 2 weeks) for 1 year, then every 6 months (\pm 2 weeks) for 2 years, then once a year (\pm 2 weeks) for 2 years for a total of 5 years, then as clinically indicated. The follow up period will begin at the end of study evaluation visit for patients that became ineligible for transplant for any reason but did not meet criteria for disease progression. The follow up period for patients that go on to transplant will begin at the Day +100 bone marrow biopsy.
- 4 At least every 4 months (\pm 1 week) for 1 year, then every 6 months (\pm 1 week) for 2 years, then once a year (\pm 2 weeks) for 2 years for a total of 5 years from study entry, then as clinically indicated. The follow up period will start at the Day 100 bone marrow biopsy in patients that received a transplant. Patients that progress will be followed for survival status only on a yearly basis.
- 5 If there is a greater than 10% difference in weight from baseline, then recalculate the BSA prior to each treatment; otherwise the actual dose given does not need to change.
- 6 CT Scan to be completed within 28 days prior to enrollment
- 7 When clinically appropriate.
- 8 CBC with differential and platelet counts will be monitored 3 times per week in between cycles of C-R-ICE until count recovery.
- 9 Days 1, 2, 8, and 9
- 10 All patients must be screened for hepatitis B infection (HBsAg/HBcAb) before starting treatment. Patients tested positive for HBV surface antigen are ineligible. Patients tested HBsAg negative/HBcAb positive should have qualitative HBV DNA PCR testing. If HBV DNA is positive the subject is excluded. If HBV DNA is negative, subject may be included but must undergo at least every 2 months HBV DNA PCR

testing from the start of treatment throughout the duration the treatment course. Monitoring during the on treatment periods is required at least every 2 months and during follow-up at a minimum of every 2 - 3 months up to 6 months after the last dose. Prophylactic antiviral may be initiated at the discretion of the investigator.

- 11 All patients must be screened for HCV infection before starting treatment. Patients who test positive for HCV antibody (Ab) evaluation of LFT's and clinical evaluation to rule out cirrhosis.
- 12 To be completed within 7 days prior to enrollment.

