10.4 Duration of Overall Survival

Duration of Overall Survival is measured from the start of treatment until death for any reason (cause of death will be documented whenever possible). Patients that progress at any time will be followed for survival only, on a yearly basis either by review of medical records or a phone call.

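### After year 5, required survival follow-up depends on progression status and Section 13.5.3 sets no horizon or common cut-off for OS, so late Kaplan-Meier OS can be biased downward

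*Combined protocol and SAP*

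**What the plan says.** Patients without progression: Table 3, footnote 4 schedules visits "for 2 years for a total of 5 years from study entry, then as clinically indicated". The synopsis (Study Procedures) and footnote 3 give the same sequence of visits and the same open ending. No section requires a check of vital status after year 5 for a patient who has not progressed.

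Patients with progression: footnote 4 adds "Patients that progress will be followed for survival status only on a yearly basis". Section 10.4 says "Patients that progress at any time will be followed for survival only, on a yearly basis", naming record review or a phone call as the method. The synopsis agrees. None of the three gives an end date.

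Analysis: Section 10.4 measures OS from start of treatment to death from any cause. Section 13.5.3 applies Kaplan-Meier with median survival, log-rank tests and Cox regression, and states "It is assumed a priori that any drop out times will be non-informative in terms of the censoring mechanism". It gives no OS censoring rule, horizon or data cut-off.

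Duration: Section 4.2 says "Accrual is expected to take up to 10 years", so patients entered early can be observed well past year 5.

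**The concern.** Kaplan-Meier needs the patients still under observation at each time to represent everyone still alive at that time, whatever the reason for censoring. Up to year 5 the schedule keeps both groups under survival follow-up. After year 5 it requires follow-up only of patients who have progressed, and these have the higher death rate. A patient whose progression is found after year 5 also enters yearly survival follow-up, while one in continued remission has no required contact.

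If long-term remissions drop out of the risk set at year 5, each later death is divided by a small group made up mainly of progressed patients, and the curve falls too fast. At stake are OS estimates beyond 5 years, the median if it lies beyond year 5, and any log-rank or Cox comparison that uses late follow-up.

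**Working it through.** The plan states no figure on this point, so there is none to reproduce. The check covers the direction and size of the effect.

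**Inputs from the documents.** Up to 30 evaluable patients (13.5.2). Accrual of up to 10 years (4.2). A 3-year PFS of 30% after salvage and transplant (Section 2, Rationale).

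**Assumptions not in the documents.** Uniform accrual. Data cut 5 years after last entry. A fraction c = 0.9 × P3 never progresses, where P3 is the 3-year progression-free proportion. The rest progress at constant rate λ = −ln[(P3 − c)/(1 − c)]/3. For P3 = 0.30, c = 0.27 and λ = −ln(0.03/0.73)/3 = 1.06 per year. Death without progression occurs at 1.5% per year. Median survival after progression is 1 or 2 years. P3 is 30%, 45% or 60%; only 30% comes from the documents. A proportion q of patients progression-free at year 5 keep a known vital status; the others are censored at year 5.

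**Mechanism.** Each death multiplies the curve by 1 − 1/n, with n the number at risk. At P3 = 30% and 1-year post-progression median, on average 7.6 progression-free and 1.5 progressed patients of 30 are alive at year 5. Rounding to 8 and 2, the next death multiplies the curve by 1 − 1/10 = 0.90 if all are observed, but by 1 − 1/2 = 0.50 if only the progressed are.

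**Simulation** (4,000 trials of 30 per row): mean Kaplan-Meier 8-year OS in %, shortfall against equal follow-up in parentheses.

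| P3 | Post-progression median | Equal follow-up | q = 0 | q = 0.5 | q = 0.9 |
|---|---|---|---|---|---|
| 30% | 1 y | 24.6 | 9.7 (14.9) | 21.7 (2.9) | 24.2 (0.4) |
| 30% | 2 y | 29.8 | 14.8 (15.0) | 25.4 (4.4) | 29.2 (0.6) |
| 45% | 1 y | 36.8 | 15.1 (21.7) | 33.5 (3.3) | 36.4 (0.4) |
| 45% | 2 y | 41.4 | 19.2 (22.2) | 36.3 (5.1) | 40.7 (0.7) |
| 60% | 1 y | 48.8 | 20.2 (28.6) | 45.5 (3.3) | 48.4 (0.4) |
| 60% | 2 y | 52.7 | 23.6 (29.1) | 47.5 (5.2) | 52.0 (0.7) |

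In every row the 5-year estimate is the same for all q.

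**Median OS** (typical value, equal follow-up against q = 0). At P3 = 30% it is 2.8 or 4.2 years and does not change. At 45% it is 4.1 years unchanged, or 5.8 against 5.3. At 60% it is 7.2 against 5.6, or 9.2 against 5.8. It moves only where it lies beyond year 5.

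**Sensitivity to the model.** A second large-sample model used P3 = 30%, 20% never progressing, post-progression median 0.5 to 2 years, death without progression at 1% or 3% per year, and a data cut 20 years after first entry. It gives shortfalls of 11 to 19 points (q = 0), 1 to 4 points (q = 0.5) and under 1 point (q = 0.9). One case can be checked by hand. With post-progression median 1 year and 1% yearly mortality, 5-year OS is 29.6%. If only progressed patients are observed afterwards, 8-year OS is 0.296 × 2⁻³ × e^(−0.03) = 0.036, or 3.6%, against 20.3% with common follow-up.

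**The case against.** The strongest objection is that the documents do not say follow-up stops at 5 years, though a reader might infer it. Footnote 4 sets minimum visit intervals, and it and footnote 23 (CT scans) continue as clinically indicated after year 5. Section 10.4 puts no limit on OS. This stands: scheduled visits end, but observation is not stated to end. The bias is therefore conditional, and the 15-to-29-point range is the extreme case of no later contact. What remains is that contact after year 5 is permitted but not required for one group, while it is required for the other. Contact prompted by clinical need also need not be random; if it favours sicker patients, the random-contact figures understate the shortfall.

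The survival-only sentence in footnote 4 could be read as applying within the same 5-year frame. The text does not settle this. On that reading the imbalance disappears, but Section 10.4 and the synopsis carry no such limit, so it would have to be written down.

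A reader might also take the non-informative drop-out sentence as contradicted outright. It concerns drop-out, not the end of scheduled visits. The gap is the follow-up rule and the missing OS censoring rule.

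Finally, a reader might infer from the Phase I response rate of 90% (13.1.2) that median OS will be understated. A response rate does not establish 5-year OS above 50%, and at the documented 30% PFS the simulated median falls before year 5.

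**Conclusion.** The point holds as a conditional one. After year 5, required survival follow-up depends on progression, and 13.5.3 has no horizon or common cut-off to prevent this from entering the OS estimate. Under the stated models, the 8-year shortfall is about 15 to 29 points if no progression-free patient is observed after year 5, 3 to 5 points if a random half are, and under 1 point at 90%. At the documented 3-year PFS of 30%, the extreme figure is about 15 points; the upper end needs a PFS twice that. The size rests on assumed survival curves, an assumed data cut and an unknown retained fraction.

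OS to 5 years, any median reached before year 5, and the response-rate test in 13.5.2 are unaffected. No PFS bias is shown, because patients still at risk for PFS all follow the same schedule. Severity is minor: OS is a secondary endpoint in about 30 patients.

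A related wording conflict is real. For transplanted patients, footnote 4 counts 5 years from study entry yet starts follow-up at the Day 100 biopsy. Footnote 3 runs 1 + 2 + 2 years from Day +100. These give different end dates.

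**What to change.** In 13.5.3, adopt one of two rules:

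- Censor OS at 5 years from start of treatment for every patient, whatever their progression status. Report 5-year OS, and give the median as not reached if the curve stays above 50%.
- Extend the yearly record review or phone call in 10.4 to progression-free patients, up to one common data cut-off stated in 13.5.3.

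Do not cap PFS on this ground. State one starting point for the 5-year period and use it in footnotes 3 and 4 and in the synopsis.

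The cost is a sentence in 13.5.3 and matching wording in 10.4, the synopsis and the footnotes. Under the first rule, OS beyond 5 years is not reported. Under the second, a yearly record check is added for the progression-free patients; in the simulations that is about 8 to 15 of 30 at year 5.
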